### **13.3. Vital Signs**

Vital signs (including systolic and diastolic blood pressure (BP), heart rate, respiratory rate, temperature, and weight) will be summarized by treatment group for the safety population and safety – Extension Study Period subset at each scheduled collection time. Change from baseline will also be summarized for all post-first infusion scheduled collection times. Baseline will be the last available measurement prior to the first infusion. All vital sign data will be listed for safety population.

### **13.4. Electrocardiogram (ECG)**

Findings of 12-lead ECG will be classified as either “Normal”, “Abnormal, not clinically significant”, and “Abnormal, clinically significant”. The number and percentage of patients will be provided, by treatment group and visit, in the form of a shift table to detect changes from baseline for safety population and safety – Extension Study Period subset. All ECG data will be listed by treatment group and visit for safety population.

### **13.5. Hypersensitivity Monitoring**

#### **13.5.1. Vital Signs**

Hypersensitivity will be assessed by vital sign monitoring except for weight on each dosing day and recorded on each dosing day at the following time points:

- Before administration (within 15 minutes prior to the beginning of the study drug infusion)
- Within 15 minutes after the end of the study drug infusion
- 1 hour ( $\pm$ 15 minutes) after the end of the study drug infusion

The number and percentage of patients who have clinically notable vital sign hypersensitivity result at the start of the infusion or any subsequent time point during hypersensitivity monitoring will be presented by treatment group, parameter, and time point. The criteria for clinically notable results are defined as follows:

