• Diagnosis of Anaphylactic Reactions

According to the Guideline for healthcare providers the following symptoms are indicative for anaphylactic reactions:

Anaphylaxis is highly likely when any one of the following 3 criteria is fulfilled:

Acute onset of an illness (minutes to several hours) with involvement of the skin, mucosal tissue, or both (e.g., generalized hives, pruritus or flushing, swollen lipstongue-uvula)

AND AT LEAST ONE OF THE FOLLOWING

- Respiratory compromise (e.g., dyspnea, wheeze-bronchospasm, stridor, reduced PEF (peak expiratory flow), hypoxemia)
- Reduced blood pressure or associated symptoms of end-organ dysfunction (e.g., hypotonia [collapse], syncope, incontinence)
- Two or more of the following that occur rapidly after exposure to a likely allergen for that subject (minutes to several hours):

- Involvement of the skin- mucosal tissue (e.g., generalized hives, itch-flush, swollen lips-tongue-uvula)
- Respiratory compromise (e.g., dyspnea, wheeze-bronchospasm, stridor, reduced PEF, hypoxemia)
- Reduced blood pressure or associated symptoms (e.g., hypotonia [collapse], syncope, incontinence)
- Persistent gastrointestinal symptoms (e.g., crampy abdominal pain, vomiting)
- Reduced blood pressure (BP) after exposure to known allergen for that subject (minutes to several hours):
 - Systolic BP of less than 90 mm Hg or greater than 30% decrease from that person's baseline
- Infection

All infections are considered AEs of special interest and include but are not limited to serious, including fatal, bacterial including tuberculosis, fungal, and new or reactivated viral infections. New or reactivated viral infections include cytomegalovirus, herpes simplex virus, parvovirus B19, varicella zoster virus, West Nile virus, and hepatitis B and C.

Serious Adverse Event

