**Table 8: Hypersensitivity Classification for Vital Signs**

Parameter	Low	High
Systolic blood pressure (mmHg)	<= 90	>= 160
Diastolic blood pressure (mmHg)	<= 50	>= 90
Respiratory rate (breaths per minute)	<= 12	>= 20
Heart rate (beats per minute)	<= 50	>= 100
Body temperature (°C)	<= 35.0	>= 38.0

All hypersensitivity vital sign data will be listed by treatment group and time point.

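### The hypersensitivity vital-sign table uses absolute cut-offs only, so its post-infusion counts include values already abnormal before that infusion and omit some large systolic falls

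*SAP*

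**What the plan says.** SAP 13.5.1 sets three readings on each dosing day: pre-dose ("Before administration (within 15 minutes prior to the beginning of the study drug infusion"), within 15 minutes after the end of infusion, and 1 hour after it. The output is the number and percentage of patients with a "clinically notable vital sign hypersensitivity result at the start of the infusion or any subsequent time point during hypersensitivity monitoring", and these figures "will be presented by treatment group, parameter, and time point".

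Table 8 ("Hypersensitivity Classification for Vital Signs") defines notable by one Low and one High limit per parameter. The systolic row reads "Systolic blood pressure (mmHg) <= 90 >= 160". For respiratory rate, 12 or below is Low and 20 or above is High. No row refers to change from an earlier reading.

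Other sections bear on the point:
- SAP 13.5.2 covers the ECG part of the same monitoring and uses a shift table against baseline.
- SAP 13.3 summarizes change in routine vital signs from a baseline taken before the first infusion.
- Protocol 7.4 lists hypersensitivity monitoring by vital signs among the secondary safety endpoints.
- Protocol 6.5.10.1, in its diagnostic criteria for anaphylaxis, includes "Systolic BP of less than 90 mm Hg or greater than 30% decrease from that person's baseline".

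**The concern.** The table is meant to describe what happens to vital signs around an infusion, but its rule describes only the level. Two consequences follow for the post-infusion cells, which are the ones that matter.

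First, a patient whose value was outside the limits before the infusion and has not moved is counted as having a hypersensitivity result afterwards. Protocol 4.1.2 excludes only uncontrolled hypertension, at the investigator's discretion, so raised pre-dose pressures can be expected.

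Second, a large fall from a high starting pressure can end inside the limits and not be counted.

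In a similarity trial the first effect is not neutral. Background counts that randomization spreads evenly over the arms pull the ratio of the two proportions towards 1. The table then looks more alike across arms than the within-infusion changes may be.

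**Working it through.** The plan states no figure for this table, so there is nothing to reproduce. The check compares the Table 8 rule with a change-based rule.

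**Inputs.** Table 8 systolic limits: Low at 90 or below, High at 160 or above. Relative fall: more than 30%, the threshold in Protocol 6.5.10.1. The pre-dose distribution is not in the documents; a normal distribution with mean 120 to 140 and SD 15 mmHg is assumed.

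**1. Unchanged values that are counted.** A patient at 165 mmHg pre-dose and 165 after the infusion has 0% change and is High at each time point. A patient going from 92 to 90 has a fall of 2/92 = 2.2% and becomes Low.

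**2. Large falls that are not counted.** A fall of more than 30% from pre-dose value B ends below 0.70 × B. It escapes the Low flag only if it ends above 90, so B must exceed 90/0.70 = 128.6. In whole mmHg:
- B = 130: 0.70 × 130 = 91.0, so the fall ends at 90 or lower and is already flagged.
- B = 131: 0.70 × 131 = 91.7, so a reading of 91 is a fall of 40/131 = 30.5% and is not flagged.

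The blind zone therefore starts at 131 and widens with B:

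| Pre-dose systolic (mmHg) | Post-infusion values that are a fall above 30% but not flagged |
|---|---|
| 130 or below | none |
| 140 | 91 to 97 |
| 150 | 91 to 104 |
| 160 | 91 to 111 |
| 170 | 91 to 118 |

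For example, 150 to 100 is a fall of 50/150 = 33% and is not counted.

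**3. How many patients could be in the blind zone.** P(B ≥ 131), with continuity cut 130.5:
- mean 120: z = (130.5 − 120)/15 = 0.70, probability 0.24
- mean 140: z = (130.5 − 140)/15 = −0.63, probability 0.74

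This is the share for whom a miss is possible. It is not the share with a missed fall.

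**4. Dilution.** Let b be the share, equal in both arms, already notable pre-dose and still notable after the infusion. Let p1 and p2 be the shares newly notable among the rest. The table compares b + (1 − b)p1 with b + (1 − b)p2. The difference is (1 − b)(p1 − p2), and the ratio moves towards 1 as b grows. The documents do not give b. As a guide to pre-dose flags only: respiratory rate is unflagged only from 13 to 19. With an assumed mean of 16 to 18, SD of 2 to 3 and rounding to whole breaths, 8% (mean 16, SD 2) to 34% (mean 18, SD 3) of pre-dose readings would be flagged.

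**The case against.** The strongest answer is that this is a supplementary display and not how the trial detects reactions. Infusion-related, hypersensitivity and anaphylactic reactions, with hypotension named among them, go on a dedicated form (Protocol 6.5.10.1). SAP 13.1.4.3 summarizes infusion-related reactions by course, relationship and intensity, and by antibody status. All monitoring values are listed. With three readings per infusion, a brief mid-infusion fall would be missed under any rule. This stands, and it limits the point to a minor one. It does not make the table informative: adverse-event entry depends on the investigator's attribution, and a listing is not an arm comparison.

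Display by time point also helps, because the pre-dose counts can be read separately. It does not remove the same patients from the post-infusion cells. Nor does SAP 13.3 fill the gap. Its baseline precedes the first infusion and it counts no large falls. The schedule of events places the routine dosing-day reading before the infusion.

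A reader might infer that the SAP breaches a protocol rule by leaving out the 30% fall. The documents do not support that. The 30% fall belongs to one of three alternative criteria for diagnosing anaphylaxis ("Anaphylaxis is highly likely when any one of the following 3 criteria is fulfilled"), applies after exposure to a known allergen, and is not assigned to this table. The protocol sets no cut-offs for the vital-sign display.

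**Conclusion.** The point holds at minor severity. As specified, the post-infusion cells mix values carried over from before the infusion with new ones. They also omit systolic falls of more than 30% that end above 90 mmHg, which is possible from a pre-dose value of 131 upwards. The 24% to 74% range rests on the assumed mean and SD, and the carry-over share cannot be computed from the documents.

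Three stronger conclusions are not supported:
- That background values dominate the comparison: no vital-sign distribution is given.
- That reactions go unrecorded: they are collected as adverse events.
- That every pre-dose flag precedes all study drug: this is true only at Week 0, since later pre-dose readings follow earlier infusions.

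No primary analysis, sample size or error rate is affected.

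**What to change.** In SAP 13.5.1:

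1. For each infusion, and separately for Low and High, count a patient as treatment-emergent when an end-of-infusion or 1-hour value is notable in a direction in which that infusion's pre-dose value was not. A Low/Normal/High shift table from pre-dose to post-infusion would serve equally and would match SAP 13.5.2. Keeping the directions separate matters: otherwise a patient who goes from High before the infusion to Low after it would be lost.
2. Show pre-dose counts as reference only.
3. Add a descriptive row for a systolic fall of more than 30% from that infusion's pre-dose value. State that the threshold is borrowed from the anaphylaxis criteria in Protocol 6.5.10.1, which refer to the person's baseline and do not assign it to this table. Note also that the pre-dose reading, taken within 15 minutes of the infusion, follows the premedication scheduled 30 minutes or more before it (Protocol 5.2.2).
4. Keep the present absolute table as a supplement.

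The cost is SAP wording and one extra table from data already collected. The drawback is small counts per cell. Nothing changes in dosing, visits or data collection.

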**Table 8: Hypersensitivity Classification for Vital Signs**

Parameter	Low	High
Systolic blood pressure (mmHg)	<= 90	>= 160
Diastolic blood pressure (mmHg)	<= 50	>= 90
Respiratory rate (breaths per minute)	<= 12	>= 20
Heart rate (beats per minute)	<= 50	>= 100
Body temperature (°C)	<= 35.0	>= 38.0

All hypersensitivity vital sign data will be listed by treatment group and time point.

### **13.5.2. Electrocardiograms**

In addition, hypersensitivity should be monitored by routine continuous clinical monitoring including 12-lead ECG monitoring 1 hour ( $\pm 15$  minutes) after the end of the study treatment infusion. Findings will be classified as either “Normal”, “Abnormal, not clinically significant”, or “Abnormal, clinically significant”. The number and percentage of patients will be provided, by treatment group and visit for the safety population and safety – Extension Study Period subset, in the form of a shift table to detect changes from baseline.

All hypersensitivity data will be listed by treatment group and time point.

### **13.6. Physical Examination**

The following body systems will be examined:

- General Appearance
- Head, Ears, Eyes, Nose, Throat
- Neck and Thyroid
- Skin
- Cardiovascular System
- Respiratory System
- Abdominal System
- Neurological System
- Musculoskeletal System (except RA symptoms)
- Lymph Nodes
- Other

Findings will be classified as either normal or abnormal. The number and percentage of patients will be provided by body system, treatment group and visit, in the form of a shift table to detect changes from baseline for safety population and safety – Extension Study Period subset. All physical examination data will be listed for safety population.

### **13.7. Immunogenicity (Anti-drug antibodies and Neutralizing antibody)**

Blood samples for immunogenicity (ADA and NAb) assessment will be obtained at Week 0 Day 0, Week 24, Week 48, Extension Week 0, Extension Week 8, Extension Week 16, Extension Week 24 and EOS (if patient withdraws prior to study completion). Immunogenicity assessment consists of both ADA and NAb assay.

ADA assay will follow a three-tiered approach consisting of (i) a screening assay, (ii) specificity/confirmatory assay and (iii) titration. The test outcome for the screening assay will be: {'Potential Positive' or 'Negative'}. Samples that are 'Potential Positive' in the screening assay will be undergone further testing in the confirmatory (immunodepletion) assay to determine if patients are a true positive. The test outcome for the screening or specificity/confirmatory assay will be: {'Reactive', 'Negative' and 'N/A'}. 'Reactive' indicates a true positive test outcome and will be labeled as 'Positive' in outputs, 'Negative' is considered negative, and 'N/A' indicates the assay was negative at the screening phase of the process. Patients with a 'Negative' test outcome for either screening or specificity/confirmatory assay will be considered negative for the overall ADA assessment. For further characterization, the antibody level will be assessed by titration in confirmed positive samples.

Samples that are positive in the ADA assay will be analyzed further to conduct a NAb assessment. The test outcome for the screening assay will be: {'Reactive', 'Rejected for Hemolysis (HEM)', 'Insufficient Sample Volume (ISV)', and 'Negative'}. Samples that are 'Reactive' in the screening assay will be undergone further testing in the confirmatory (immunodepletion) assay to determine if patients were a true positive. The test outcome for the confirmatory assay will be: {'Positive', 'Negative' and 'N/A'}. 'Positive' indicates a true positive test outcome, 'Negative' is considered negative, and 'N/A' indicates the assay was negative at the screening phase of the process. Patients with a 'Negative' test outcome for either the screening or confirmatory assay will be considered negative for the overall NAb assessment. ADA assay will be performed using the labelled antibody with CT-P10, Rituxan and MabThera tag for Part 1 patients up to Week 24, whereas a single labelled antibody with CT-P10 tag will be used for the assessment of patients in Part 2 up to Week 48 and patients in Extension Study Period.

### **13.7.1. Summary of ADA and NAb**

The results of the ADA assay will be summarized by each assay tag. The number and percentage of patients will be presented at each scheduled visit the assessments took place, by treatment group. A listing of the ADA assay will be presented by the part, visit, tag type and treatment group. Tables will be produced for the safety population, safety - 2nd treatment course in Main Study Period subset and safety – Extension Study Period subset. Listings will be produced for the safety population.

Regarding the NAb assay, all patients in Part 1 and Part 2 will be tested in the determination of NAb using a single antibody. The results of the NAb assay will be summarized. The number and percentage of patients will be presented at each scheduled visit the assessments took place, by part and treatment group. The outcome of NAb will be listed by treatment group. Tables will be produced for the safety population, safety - 2nd treatment course in Main Study Period subset and safety – Extension Study Period subset. Listings will be produced for the safety population.

### **13.7.2. Evaluation of Tag Concordance of ADA Assessments**

For the Part 1, the evaluation of Tag concordance of both ADA assessments (tagged with CT-P10 versus Rituxan, CT-P10 versus MabThera, Rituxan versus MabThera) will be evaluated for Week 0 Day 0 and Week 24.

The agreement in outcome between both assays will be evaluated using three methods that are commonly used to compare diagnostic tests when no standard reference test is available [14]:

- Positive percent agreement (PPA)
  - (Number of patients with positive outcome for both CT-P10 and Rituxan tags)/ (Number of patients with positive outcome for Rituxan tag) \* 100
  - (Number of patients with positive outcome for both CT-P10 and MabThera tags)/ (Number of patients with positive outcome for MabThera tag) \* 100
  - (Number of patients with positive outcome for both MabThera and Rituxan tags)/ (Number of patients with positive outcome for Rituxan tag) \* 100
- Negative percent agreement (NPA)
  - (Number of patients with negative outcome for both CT-P10 and Rituxan tags)/ (Number of patients with negative outcome for Rituxan tag) \* 100
  - (Number of patients with negative outcome for both CT-P10 and MabThera tags)/ (Number of patients with negative outcome for MabThera tag) \* 100
  - (Number of patients with negative outcome for both MabThera and Rituxan tags)/ (Number of patients with negative outcome for Rituxan tag) \* 100
- Cohen's Kappa statistic: the Kappa statistic is a measure of the overall agreement.

Higher percentages of PPA and NPA indicate a stronger agreement between outcomes. A higher value of the Kappa statistic indicates a stronger agreement between outcomes, with a value of 1 implying complete agreement.

The table analyzing ADA test agreement by treatment group and visit will be provided containing a cross-tabulation of test outcomes (for the CT-P10 and MabThera, CT-P10 and Rituxan, Rituxan and MabThera tagged assays), and the Kappa statistics with a 95% CI and corresponding p-value. If missing values (i.e. patients with no assessment or only one reported result from assessments) are present, the number of missing values will also be tabulated but will be excluded when deriving the PPA, NPA and Kappa statistics.

### **13.7.3. ADA titer Results**

ADA titer values of the CT-P10, Rituxan and MabThera tagged assay for the Part 1 patients up to Week 24 and ADA titer values of the CT-P10 tagged assay for the Part 2 patients up to Week 48 and Extension Study Period patients will be transformed using a  $[\log_2 x] + 1$  transformation. If the values in the data are in inequality forms, the sign of inequality will be removed and then the values will be transformed. Descriptive statistics of transformed ADA titer will be displayed for Week 0 Day 0, Week 24, Week 48, Extension Week 0, Extension Week 8, Extension Week 16, Extension Week 24 visit by treatment group on the safety population, safety – 2nd treatment course in Main Study Period subset and safety – Extension Study Period subset. The transformed results of ADA titer for each visit will also be listed by treatment group.

### **13.8. Interferon-gamma Release Assay**

Interferon gamma release assay (IGRA) will be conducted at Baseline and results will be classified as “Positive”, “Indeterminate” or “Negative”. If a patient has an unscheduled screening visit, the results from the visit with the latest date will be reported as “Baseline”. All results from visits will be reported in a “During the study period” category using the following methodology:

- If a patient has at least one result of “Positive” in the Study Period they will be considered as “Positive”

- If a patient has no “Positive” results and at least one result of “Indeterminate” in the Study Period then they will be considered as “Indeterminate”
- If a patient has no “Positive” and no “Indeterminate” results in the Study Period then they will be considered as “Negative”

The number and percentage of patients with each result will be provided by treatment group for Baseline visit and study period for the safety population and safety – Extension Study Period subset. A listing displaying each patient’s IGRA results will be provided by treatment group and visit.

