6.5.6 Tuberculosis Assessment

At Screening, a current or past diagnosis of TB, recent exposure to person with active TB, or examination findings indicating the presence of TB, defined as a positive result for interferon- γ release assay, will result in patient exclusion from the study. A patient with sufficient documentation of prophylaxis or complete resolution following treatment can be enrolled. Signs and symptoms of TB will be monitored throughout the study, and interferon- γ release assay can be performed at the investigator's discretion based on the judgment on the signs and symptoms of TB monitoring.

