## 5. General Statistical Considerations

Continuous data will be summarized using descriptive statistics: n, mean, standard deviation (SD), median, minimum and maximum, unless otherwise indicated. Minimum and maximum will be presented to the same number of decimal places as the raw data, mean and median will be presented to one more decimal place than the raw data, and SD will be presented to two more decimal places than the raw data. If the geometric mean is to be presented, it will be set to the same precision as the mean. Percent coefficient of variation (CV) will be presented to one decimal place. P-values will be rounded to three decimal places. If a p-value is less than 0.001 it will be reported as “<0.001”. If a p-value is greater than 0.999 it will be reported as “>0.999”.

Categorical data will be summarized using counts and percentages. Percentages will be suppressed when the count is zero. A row denoted “Missing” will be included in count tabulations where necessary to account for missing values. The denominator for all percentages will be the number of patients within the treatment group for the all populations. Percentages will be presented to one decimal place.

Unless otherwise specified, summaries for visit-based data will only display scheduled visits.

Confidence intervals obtained from statistical procedures will be displayed to the same number of decimal places as the associated estimate.

All data will be displayed in listings. Unless otherwise specified, listings will be sorted by the treatment group, patient number, and assessment date or visit date, if applicable. In cases where more ordering is required, other variables will be included in the sort order as applicable.

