In total, approximately 361 patients will be available for analysis (a total of approximately 149 patients for the CT-P10 group and 212 patients for the reference products group, including up to 63 patients from each treatment group in Part 1).

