11. Interferon- $\gamma$  release assay will be performed at Screening and Week 48 (or End-of-Study Visit). The results of the test should be entered in the electronic case report form. Throughout the study, patients will be monitored for the clinical signs and symptoms of TB, and interferon- $\gamma$  release assay can be performed at the investigator's discretion based on the judgment on the signs and symptoms of TB monitoring.
12. One image of each hand and each foot (both the right and left hands and feet, a total of 4 images) for analysis of efficacy will be obtained at the scheduled times. Joint damage, as determined by radiography, will be assessed by change in the van der Heijde modification of the Sharp scoring system. The baseline radiographs must be assessed within 42 days prior to the randomization date. Hand and foot x-rays will be evaluated centrally by an independent reviewer for reporting purposes and on a local level for treatment practice.
13. ACR20, ACR50, ACR70, and hybrid ACR will be calculated from these assessments. It is recommended that the joint count assessments are performed by the same physician when possible.
14. The European League Against Rheumatism response criteria will be derived from the DAS28.
15. Immunoglobulin (IgM, IgG and IgA) testing will be performed at the central laboratory.
16. Patients with B-cell, IgM and IgG values below the LLN or less than 50% of their baseline value should be monitored every 8 weeks after the study completion until recovery is achieved for one of them (equal to or higher than the lower limit of normal OR at least 50% of the baseline value). Upon the study completion, additional follow-up of B-cell, IgM and IgG monitoring will be determined by the Data Safety Monitoring Board (DSMB).

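### SAP 13.8 classes patients with no study-period IGRA result as Negative, so the safety summary does not separate untested patients from those who tested negative

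*SAP*

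**What the plan says.** SAP 13.8 states that the assay "will be conducted at Baseline and results will be classified as" Positive, Indeterminate or Negative. For a separate study-period category it applies three steps:

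- any Positive result makes the patient *Positive*;
- failing that, any Indeterminate result makes the patient *Indeterminate*;
- patients with neither kind of "results in the Study Period then they will be considered as" *Negative*.

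Counts and percentages are given by treatment group "for Baseline visit and study period for the safety population and safety" Extension Study Period subset. A listing of each patient's results by visit is also planned.

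Two general rules in SAP section 5 bear on the table. One is "The denominator for all percentages will be the number of patients within the treatment group for the all populations". The other is that a row for missing data "will be included in count tabulations where necessary to account for missing values".

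On timing, protocol 6.5.6 tests at Screening and says that afterwards the "release assay can be performed at the investigator's discretion based on the judgment on the signs and symptoms of TB monitoring". The footnotes to protocol Tables 4, 5 and 6 say the same about later testing. SAP Appendix 1 agrees for one-course patients (footnote 8) and for the Extension (footnote 15). For two-course patients, however, its footnote 11 says that the "release assay will be performed at Screening and Week 48 (or End-of-Study Visit").

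**The concern.** The *Negative* step is defined by the absence of other results, not by the presence of a negative one. A patient with no study-period test satisfies it. Because later testing is discretionary, such patients arise from the design and not only from missed visits.

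Two things follow for the summary table. Its *Negative* row mixes patients who tested negative with patients for whom there is no result. And it can create an apparent change. Protocol 6.5.6 allows enrolment of patients with documented prophylaxis or complete resolution, and SAP 13.8 provides for Positive and Indeterminate results at Baseline. A patient in either class who is never retested would be shown under that class at Baseline and as *Negative* during the study.

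TB signs and symptoms are a listed safety endpoint (protocol 7.4), and tuberculosis is named among the infections of special interest (SAP 13.1.4.1). A reader of this table should be able to tell how many patients were tested.

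**Working it through.** The plan states no figure on this point, so there is nothing to reproduce. The check has three steps.

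**1. Apply the rule to each kind of patient.** The second column follows SAP 13.8 as written. The third also requires at least one post-baseline result for *Negative*.

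| Study-period results | SAP 13.8 | With a result required |
|---|---|---|
| none | Negative | Not tested |
| one Negative | Negative | Negative |
| Indeterminate and Negative | Indeterminate | Indeterminate |
| Positive and Negative | Positive | Positive |

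Only the patient with no result changes class.

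**2. Ask who can have no result.**

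| Patients | Protocol | SAP |
|---|---|---|
| Two courses | Screening, then discretionary (Table 4, footnote 11) | Screening and Week 48 or End-of-Study (Appendix 1, footnote 11); 13.8 names Baseline only |
| One course | discretionary (Table 5) | discretionary (Appendix 1, footnote 8) |
| Extension | discretionary (Table 6, footnote 15) | discretionary (Appendix 1, footnote 15) |

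The only routine later test is in SAP footnote 11. It conflicts with the protocol and with SAP 13.8, and it covers only the two-course schedule.

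Counting the Screening result as a study-period result would not repair the rule. Protocol 3.1 lists Screening separately from the Study Periods, and a pre-treatment result would then be reported as an on-study one.

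**3. Count the patients affected.** Let N be the number in the table, f the share retested at least once and T = f × N, rounded. Untested patients in the *Negative* row = N − T. SAP 5.2 gives the planned size: "In total, approximately 361 patients will be available for analysis". I use 361 as a stand-in for the safety population. The values of f are assumptions.

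| f | T | Untested, counted as Negative | Share of 361 |
|---|---|---|---|
| 5% | 18 | 361 − 18 = 343 | 95.0% |
| 10% | 36 | 361 − 36 = 325 | 90.0% |
| 25% | 90 | 361 − 90 = 271 | 75.1% |
| 50% | 180 | 361 − 180 = 181 | 50.1% |
| 80% | 289 | 361 − 289 = 72 | 19.9% |
| 100% | 361 | 0 | 0% |

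At f = 50% the split is 149 − 74 = 75 untested on CT-P10 and 212 − 106 = 106 on the reference products.

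**The case against.** The best defence is that the three steps only rank results that exist. SAP 13.8 introduces them by saying that all results from visits are reported in this category. On that reading, a patient without a result goes to the general *Missing* row of SAP section 5. A programmer could reasonably do that.

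It does not settle the matter. The general row applies where values are left missing, and the third step has already given these patients a class. Elsewhere the SAP is explicit: immunoglobulin percentages use patients with a value at the visit (13.2), the RF and anti-CCP shift tables carry a missing category (12.1), ADA concordance tabulates and excludes missing values (13.7.2), and the antibody-negative subsets need a negative result (5.4). Section 13.8 has no such provision. If the milder reading is intended, the fix simply states it.

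Three other points stand and limit the concern:

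- The by-visit listing identifies the tested patients, and tuberculosis is captured separately as an infection adverse event.
- If the Week 48 or End-of-Study test in SAP footnote 11 was carried out, fewer patients are affected.
- Replacing the denominator with tested patients alone would not give a population rate, because discretionary testing follows signs and symptoms and so selects patients.

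**Conclusion.** As written, the rule counts patients with no study-period IGRA as *Negative*, and the schedule makes such patients likely. This should be corrected, but its reach is limited to one descriptive safety summary, shown for the safety population and its Extension subset. The co-primary PK and DAS28 (CRP) analyses do not use it.

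The size is the number not retested: anywhere from 343 of 361 at 5% retested to none at 100%, with 181 at 50%. These figures rest on the planned sample size and on assumed retest shares.

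A reader might go further and infer that the table understates a TB conversion rate, or that nearly all of its *Negative* entries are untested. The documents support neither. SAP 13.8 plans counts at Baseline and during the study, with no shift table and no definition of conversion, and some enrolled patients may already be positive at Baseline. The retest share is not stated anywhere. Nor do the documents explain why SAP footnote 11 differs from the protocol, so it should be treated as an inconsistency to resolve and nothing more.

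**What to change.** - In SAP 13.8, assign *Negative* only to patients with at least one post-baseline IGRA result and no Positive or Indeterminate result.
- Add a *Not tested* row to the study-period summary, for both the safety population and the Extension subset.
- Keep the all-patient denominator of SAP section 5 and show the number tested beside it. Add a footnote that later testing is discretionary and prompted by signs and symptoms, so neither percentage is a conversion rate.
- Reconcile SAP Appendix 1 footnote 11 (two-course schedule) with protocol Table 4 footnote 11 and with SAP 13.8.

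The cost is a few lines of SAP text and one revised table shell. No new data or assessments are needed.
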